3.1.11. Age  $>$  18 years

3.1.12. Men and women of childbearing potential enrolled in this study must agree to use adequate barrier birth control measures during the course of the study and up to 2 months after.

3.1.13. Written informed consent.

### **3.2 Exclusion Criteria:**

3.2.1 Patients with a history of clinically significant chronic autoimmune disease

3.2.2. Prior therapy with antibodies that modulate T-cell function defined as: anti-CTLA-4, anti-PD-1, and anti-PD-L1 drugs.

3.2.3. Conditions currently requiring immunosuppressive medications

3.2.4. Known history of HIV or hepatitis B or C

3.2.5. Bleeding diathesis or coagulopathy that in the investigators opinion would prevent ablation from being safely performed.

3.2.6. Patients with unstable angina (anginal symptoms at rest) or new-onset angina (began within the last 3 months) or myocardial infarction within the past 6 months.

3.2.7. History of organ allograft even if not taking immunosuppressive medications

3.2.8. Pregnant or breast-feeding.

**3.3 Re-screening:** If a patient signs consent and then screen fails (does not meet the eligibility criteria) and the treating MD requests that the patient be re-screened outside of the 28 day screening window, sites are to contact BrUOG who will assess patients on a case by case basis. Depending on many diverse factors including the conditions that are being evaluated, the reasons why patient initially screen failed, and the nature of the initial results, re-screening may or may not be medically/scientifically appropriate. BrUOG should be made aware of such a situation with at least 72 hours and provided with information on screen-failure.

## **4.0 TREATMENT:**

**4.1 Nivolumab:** 3mg/kg up to a maximum dose of 240mg IV over approximately 60 minutes on Day 1 +/- 3 days every 2 weeks until progression for a maximum of 2 years.

It will also not be considered a deviation if a cycle or pre-cycle assessment must be adjusted to accommodate scheduling or holidays. Adjustment must be documented with reason to BrUOG. While efforts should be made to have cycles be every 2 weeks (+/- 3 days), further allowances are allowed as long as cycles are not < 10 days.

**4.2 Ablation:** Either cryoablation or thermal ablation may be performed as per standard institutional policies. Ablation should be performed within 1 week (7 days) of the initial treatment with nivolumab, to occur within the first cycle (14 days) of treatment. Additional ablation procedures may be performed as clinically indicated such as for pain control including the treatment or prevention of pain or obstruction or as per institutional standard of care. There must be a minimum of 60 days between each ablation (60-90 days is preferable). Standard institutional procedures may be used in ablation. One or more than one lesion may undergo ablation as per investigator judgement and institutional standard of care. At least one measurable site of disease cannot be ablated so that it may be followed for response. This location should be chosen at baseline with enrollment-see section 3.1.5

During the same procedural period as ablation, if patient has consented and agreed, a tumor tissue biopsy may be obtained prior to each ablation, as per institutional standard of care. This biopsy may be assessed for future correlative studies such as assessment of PD-L1 by immunohistochemical staining and will allow for correlation to response.

The following treatments must not be administered during the study: Immunotherapy other than the study drug, immunosuppressive drugs [i.e., chemotherapy or systemic corticosteroids except for short term treatment of allergic reactions or for the treatment of immune related adverse events (irAEs)}, or other experimental pharmaceutical products. Short term administration of systemic steroid (i.e., for allergic reactions or the management of irAEs is allowed).

Growth factors (granulocyte colony stimulating factor or granulocyte macrophage colony stimulating factor). Exception: Erythropoietin and darbepoietin alpha may be prescribed at the investigator's discretion.

#### **Requirements For Ablation:**

Pre-ablation labs will be done within 2 weeks of ablation (prior to). If the counts are done early and would preclude the patient from ablation, labs should be repeated on the day of the procedure prior to cancelling.

Ablation cannot occur unless the following criteria are met:

PLT  $\geq 50 \times 10^9/L$  (50,000/mm^3)  
INR <1.8

#### **5.0 DOSE MODIFICATIONS OF NIVOLUMAB AND TOXICITY MANAGEMENT:**

Adverse events will be graded with the use of the National Cancer Institute Common Terminology Criteria for Adverse Events, version 4

## **5.1 Nivolumab Dose Modifications:**

No dose reductions of nivolumab are included in the study. Any adverse event, laboratory abnormalities, or undercurrent illness which in the judgment of the investigator, can warrant delaying the dose of study medication.

## **5.2 The following must be confirmed prior to dosing a patient with Nivolumab:**

- 1) Patients experiencing treatment related (drug) grade 4 or treatment related (drug) clinically significant grade 3 toxicities must have toxicity resolved to grade 2 or less prior to resuming nivolumab.

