## **5.3 Hold treatment until recovery to grade 1 or resolution for:**

- 1) If AST or ALT >3 to 5 times ULN (grade 2) or total bilirubin >1.5 to 3 times ULN (grade 2): **Withhold treatment**; may resume therapy upon recovery to grade 0 or 1 toxicity (AST/ALT grade 1 is >ULN-3xULN, Total bilirubin grade 1 is >ULN-1.5xULN).

\*\*for possibly, probably or definitely related to nivolumab see section 5.3, 2.I below

\*\*AST or ALT >5 times ULN (grade 3) or total bilirubin >3 times ULN (grade 3) or severe/life-threatening immune-mediated hepatitis: **Permanently discontinue**. \*\*see section 5.3 (this section), 2\*\* below

- 2) Immune-mediated hepatitis:

- I. Grade 2 or higher transaminase elevations that are possibly, probably or definitely related to nivolumab (with or without total bilirubin elevations): Withhold treatment and initiate high-dose systemic corticosteroids (prednisone 1 to 2 mg/kg daily or equivalent)

\*\* Severe (grade 3) or life-threatening (grade 4) transaminase elevations: Permanently discontinue treatment and initiate high-dose systemic corticosteroids (prednisone 1 to 2 mg/kg daily or equivalent)

- 3) **Colitis:**

- I.** Grade 2 (duration >5 days): Also administer systemic corticosteroids (prednisone 0.5 to 1 mg/kg daily or equivalent) followed by a corticosteroid taper; may increase to prednisone 1 to 2 mg/kg daily (or equivalent) if colitis worsens or does not improve despite corticosteroid use
- II.** Grade 3: Also administer systemic corticosteroids (prednisone 1 to 2 mg/kg daily or equivalent) followed by a corticosteroid taper

- 4) **Pneumonitis:** Pneumonitis (grade 2); also administer high-dose systemic corticosteroids (prednisone 1 to 2 mg/kg daily or equivalent) followed by a corticosteroid taper

- 5) **Other immune-mediated toxicities:** Other immune-mediated toxicities; also administer high-dose systemic corticosteroids followed by a corticosteroid taper (over 1 month)

- 6) **Creatinine** >1.5 to 6 times ULN (grade 2 or 3) or >1.5 times baseline (grade 1): Withhold treatment; administer prednisone 0.5 to 1 mg/kg daily (or equivalent) followed by a corticosteroid taper; may resume therapy upon recovery to grade 0 or 1 toxicity. If toxicity worsens or does not improve, permanently discontinue and increase corticosteroid dose to prednisone 1 to 2 mg/kg daily (or equivalent).

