#### 5.4 Discontinue treatment (remove patient from study), for following:

- 1) AST or ALT >5 times ULN (grade 3) or total bilirubin >3 times ULN (grade 3) or severe/life-threatening immune-mediated hepatitis: **Permanently discontinue.**
- 2) Colitis
  - I. Colitis: (grade 4); also administer high-dose systemic corticosteroids (prednisone 1 to 2 mg/kg daily or equivalent) followed by a corticosteroid taper
  - II. Colitis (recurrent)
- 3) Pneumonitis  
Pneumonitis (grade 3 or 4); also administer high-dose systemic corticosteroids (prednisone 1 to 2 mg/kg daily or equivalent) followed by a corticosteroid taper
- 4) Inability to reduce corticosteroid dose to prednisone  $\leq$ 10 mg/day (or equivalent) within 12 weeks.
- 5) Other adverse reactions that are life-threatening, severe or grade 3 treatment related adverse reactions that recur, or persistent grade 3 treatment-related toxicity that does not recover to grade 1 or resolve within 12 weeks (except alopecia)..
- 6) Creatinine >6 times ULN (grade 4): Permanently discontinue; initiate high-dose systemic corticosteroids
- 7) Severe (grade 3) or life-threatening (grade 4) transaminase elevations: Permanently discontinue treatment and initiate high-dose systemic corticosteroids (prednisone 1 to 2 mg/kg daily or equivalent)

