**For Grade 2 symptoms** (moderate reaction requires therapy or infusion interruption but respond promptly to symptomatic treatment [eg, antihistamines, non-steroidal anti-inflammatory drugs, narcotics, corticosteroids, bronchodilators, IV fluids], prophylactic medications indicated for < 24 hours) Stop the nivolumab infusion, begin an IV infusion of normal saline, and treat the subject with diphenhydramine 50 mg IV (or equivalent) and/or paracetamol 325 to 1000 mg (acetaminophen); remain at bedside and monitor subject until resolution of symptoms. Corticosteroid or bronchodilator therapy may also be administered as appropriate. If the infusion is interrupted, then restart the infusion at 50% of the original infusion rate when symptoms resolve; if no further complications ensue after 30 minutes, the rate may be increased to 100% of the original infusion rate. Monitor subject closely. If symptoms recur then no further nivolumab will be administered at that visit. Administer diphenhydramine 50 mg IV and remain at bedside and monitor the subject until resolution of symptoms. The amount of study drug infused must be recorded on the appropriate page. The following prophylactic medications are recommended for future infusions: diphenhydramine 50 mg (or equivalent) and/or paracetamol 325 to 1000 mg (acetaminophen) should be administered at least 30 minutes before additional nivolumab administration. If necessary, corticosteroids (recommended dose: up to 25 mg of IV hydrocortisone or equivalent) may be used.

**Grade 3 or 4 symptoms** (severe reaction, Grade 3 prolonged [ie not rapidly responsive to symptomatic medication and/or brief interruption of infusion]; recurrence of symptoms following initial improvement; hospitalization indicated for other clinical sequelae [eg, renal impairment, pulmonary infiltrates]). Grade 4: (life-threatening, pressor or ventilatory support indicated): Immediately discontinue infusion of nivolumab. Begin an IV infusion of normal saline and treat the subject as follows: recommend bronchodilators, epinephrine 0.2 to 1 mg of a 1:1,000 solution for subcutaneous administration or 0.1 to 0.25 mg of a 1:10,000 solution injected slowly for IV

administration, and/or diphenhydramine 50 mg IV with methylprednisolone 100 mg IV (or equivalent) as needed. Subjects should be monitored until the investigator is comfortable that the symptoms will not recur. **Nivolumab will be permanently discontinued.**

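### Section 5.2 contemplates resuming nivolumab after a drug-related grade 4 toxicity without reference to the stop rules in 5.4 and 5.7, and grade 4 events that no rule names have no single stated outcome

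*Protocol*

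**What the plan says.** Five parts of Protocol section 5 bear on a drug-related grade 4 toxicity.

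- **5.2, item 1**, headed as what has to be confirmed before a dose. It reads "Patients experiencing treatment related (drug) grade 4 or treatment related (drug) clinically significant grade 3 toxicities must have toxicity resolved to grade 2 or less", and the sentence ends by making this a condition for resuming nivolumab. It does not refer to 5.3, 5.4 or 5.7.
- **5.3**, headed as a hold until grade 1 or resolution. Item 5 covers other immune-mediated toxicities with no grade limit. Item 2 contains a stop line: "Severe (grade 3) or life-threatening (grade 4) transaminase elevations: Permanently discontinue treatment".
- **5.4**, headed "Discontinue treatment (remove patient from study), for following". It lists grade 3 or 4 transaminase elevation, grade 4 colitis, grade 3 or 4 pneumonitis and grade 4 creatinine ("Creatinine >6 times ULN (grade 4): Permanently discontinue"). Item 5 is a residual line that begins "Other adverse reactions that are life-threatening, severe or grade 3 treatment related adverse reactions that recur" and goes on to persistent grade 3 toxicity that has not recovered within 12 weeks.
- **5.5** repeats the hepatic stop rules.
- **5.7**, on grade 3 or 4 infusion reactions: "Nivolumab will be permanently discontinued".

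No sentence says which section governs when more than one applies. The SAP reproduces only the statistical section and does not touch this point.

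**The concern.** Section 5.2 is the rule a site consults on the day of dosing. It names grade 4 and speaks of resuming, so it presupposes that some patients with a drug-related grade 4 event will be dosed again. Section 5.4 removes patients for every grade 4 event it lists and, through item 5, for other life-threatening reactions. If both can apply to the same patient, re-exposure after a serious drug reaction depends on which section the site opens. In an uncontrolled study of a new combination, that is first a patient-safety matter. It also makes drug exposure and the toxicity summary harder to interpret, because sites may follow different rules.

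**Working it through.** The main check is textual. Take a drug-related grade 4 event that has since improved to grade 2 and read each section in turn.

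| Event | 5.2(1) | 5.3 | 5.4 or 5.7 |
|---|---|---|---|
| Transaminases | condition for resuming met | stop (items 1, 2) | stop (5.4 items 1, 7) |
| Colitis | met | no grade 4 line (item 3 covers grades 2 and 3) | stop (5.4 item 2) |
| Pneumonitis | met | no grade 4 line (item 4 covers grade 2) | stop (5.4 item 3) |
| Creatinine | met | no grade 4 line (item 6 goes up to grade 3) | stop (5.4 item 6) |
| Infusion reaction | met | none | stop (5.7) |
| Unnamed immune-mediated event | met | still held (item 5 needs grade 1 or resolution) | remove from study if life-threatening (5.4 item 5) |

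**Named events.** Each has an explicit stop line. A specific line is normally read as overriding a general one, so a single outcome can be recovered. The defect here is only that 5.2 mentions grade 4 without saying so.

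**Unnamed events.** Section 9.0 lists neurological, skin and endocrine immune toxicities, the last including thyroid, adrenal and pituitary. Section 5.6 deals with thyroid disorders. Neurological, skin, adrenal and pituitary events have no organ-specific grade 4 line. For these, 5.2, 5.3(5) and 5.4(5) are all general, so specific-over-general does not rank them. At grade 2, 5.2 is met and 5.3(5) is not. At grade 1, both are met. At either grade, 5.4(5) removes the patient if the reaction counted as life-threatening.

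**Does grade 4 mean life-threatening?** The text points both ways.
- Transaminases are labelled life-threatening by grade alone in 5.3, 5.4 and 5.5. Section 5.7 pairs the terms again: "Grade 4: (life-threatening, pressor or ventilatory support indicated): Immediately discontinue infusion of nivolumab".
- Section 11.1 defines life-threatening for safety reporting as immediate risk of death in the investigator's view. Grade 4 creatinine is identified by a laboratory multiple and is not called life-threatening.

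If the terms are equivalent, 5.4 and 5.7 remove every drug-related grade 4 patient and the grade 4 wording in 5.2 has no use. If they are not, 5.2 keeps a residual scope, but a site cannot tell where it ends.

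**What does the recurrence condition in 5.4(5) qualify?** It can attach to the severe or grade 3 reactions only, or to life-threatening reactions as well. The second reading is less natural. Under it, item 5 would not stop treatment after a first unnamed life-threatening reaction.

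**Size.** Section 2.0 gives 8% grade 3 or 4 treatment-related events in the NSCLC patients of the expanded phase I study, and 7% grade 3/4 toxicity with nivolumab in the non-squamous phase III trial. Section 17.1 gives 33 patients in total and 18 in stage one.

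- Full accrual: 33 × 0.07 = 2.31; 33 × 0.08 = 2.64.
- Stage one only: 18 × 0.07 = 1.26; 18 × 0.08 = 1.44.

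These are expected counts for grades 3 and 4 together. The documents give no grade 4 rate, so the grade 4 part cannot be separated. Of the three most common grade 3 and 4 events listed in section 2.0 (fatigue, elevated AST, pneumonitis), two already have explicit stop lines.

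**The case against.** The best defence is that 5.2 states a minimum condition and grants no permission. A site that obeys 5.4 breaches nothing in 5.2, whereas a site that re-doses after grade 4 colitis breaches an explicit line of 5.4. Read cumulatively, the strictest rule always wins. This stands for the named events, and a reader who infers that 5.2 leaves two equally compliant outcomes for each of them goes further than the text allows. It does not settle the unnamed events. The protocol states no strictest-rule principle, and the scope of 5.4(5) depends on a term whose meaning is left open.

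Other tempting readings also go too far:

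- **That 5.4(5) permanently stops treatment for any life-threatening reaction.** Item 5 is confined to other reactions and does not itself use the word permanently; the stop comes from the section heading.
- **That every first grade 3 event has two opposite outcomes.** The later clause of item 5 on persistent grade 3 toxicity would be redundant if a first grade 3 reaction already meant removal, so context largely settles this. First grade 3 colitis and creatinine are explicit holds; first grade 3 pneumonitis and transaminase elevation are explicit stops.
- **That trial data are materially affected.** Footnote D of the study calendar keeps CT about every 3 months, with physician discretion, for patients removed for toxicity without progression. That is close to the on-treatment interval of about 12 weeks. Follow-up runs for five years and survival is counted from study entry.

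Investigator withdrawal (section 12.0), discretionary dose delay (5.1) and DSMB review (16.0) reduce the practical risk, but they do not reconcile the text.

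**Conclusion.** The point holds as a wording inconsistency with a safety consequence. For named grade 4 events, 5.2 lacks an exception that the reader has to supply. For unnamed drug-related grade 4 immune events, three general rules can apply with different outcomes, no precedence is stated and the meaning of life-threatening is unsettled.

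The number of patients affected is unknown. It should lie below the 2 to 3 of 33 implied by the combined grade 3 and 4 rate, on the assumption that the nivolumab-alone rates carry over and ablation adds no drug-related grade 4 events. No effect on the response endpoint or on the Simon design is shown, so the case for change rests on patient safety and consistent conduct across sites. No view is taken here on which clinical rule is right.

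**What to change.** Reconcile 5.2(1), 5.3, 5.4 and 5.7, together with the hepatic text repeated in 5.5, as follows:

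1. Give each drug-related grade 4 event, named or unnamed, one stated outcome.
2. Add a sentence to 5.2 saying which section governs when more than one applies.
3. State whether life-threatening in 5.4(5) means grade 4, the section 11.1 definition, or something else.
4. Split 5.4(5) into separate lines so that it is clear which reactions the recurrence condition qualifies.

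The sponsor's medical lead decides the content of each rule. The cost is a wording amendment and a notice to sites, with IRB approval at each center if the amendment is judged to affect subject safety significantly (section 14.3). No new procedures, visits or data collection are needed, and the sample size and stopping boundaries are unchanged.

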## **5.3 Hold treatment until recovery to grade 1 or resolution for:**

- 1) If AST or ALT >3 to 5 times ULN (grade 2) or total bilirubin >1.5 to 3 times ULN (grade 2): **Withhold treatment**; may resume therapy upon recovery to grade 0 or 1 toxicity (AST/ALT grade 1 is >ULN-3xULN, Total bilirubin grade 1 is >ULN-1.5xULN).

\*\*for possibly, probably or definitely related to nivolumab see section 5.3, 2.I below

\*\*AST or ALT >5 times ULN (grade 3) or total bilirubin >3 times ULN (grade 3) or severe/life-threatening immune-mediated hepatitis: **Permanently discontinue**. \*\*see section 5.3 (this section), 2\*\* below

- 2) Immune-mediated hepatitis:

- I. Grade 2 or higher transaminase elevations that are possibly, probably or definitely related to nivolumab (with or without total bilirubin elevations): Withhold treatment and initiate high-dose systemic corticosteroids (prednisone 1 to 2 mg/kg daily or equivalent)

\*\* Severe (grade 3) or life-threatening (grade 4) transaminase elevations: Permanently discontinue treatment and initiate high-dose systemic corticosteroids (prednisone 1 to 2 mg/kg daily or equivalent)

- 3) **Colitis:**

- I.** Grade 2 (duration >5 days): Also administer systemic corticosteroids (prednisone 0.5 to 1 mg/kg daily or equivalent) followed by a corticosteroid taper; may increase to prednisone 1 to 2 mg/kg daily (or equivalent) if colitis worsens or does not improve despite corticosteroid use
- II.** Grade 3: Also administer systemic corticosteroids (prednisone 1 to 2 mg/kg daily or equivalent) followed by a corticosteroid taper

- 4) **Pneumonitis:** Pneumonitis (grade 2); also administer high-dose systemic corticosteroids (prednisone 1 to 2 mg/kg daily or equivalent) followed by a corticosteroid taper

- 5) **Other immune-mediated toxicities:** Other immune-mediated toxicities; also administer high-dose systemic corticosteroids followed by a corticosteroid taper (over 1 month)

- 6) **Creatinine** >1.5 to 6 times ULN (grade 2 or 3) or >1.5 times baseline (grade 1): Withhold treatment; administer prednisone 0.5 to 1 mg/kg daily (or equivalent) followed by a corticosteroid taper; may resume therapy upon recovery to grade 0 or 1 toxicity. If toxicity worsens or does not improve, permanently discontinue and increase corticosteroid dose to prednisone 1 to 2 mg/kg daily (or equivalent).

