## **5.6 Thyroid Disorders**

Thyroid disorder (hyperthyroidism or hypothyroidism): There are no recommended dosage modifications.

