### ***DOSAGE FORMS AND STRENGTHS***

Injection: 40 mg/4 mL (10 mg/mL) and 100 mg/10 mL (10 mg/mL) solution in a single-use vial.

Dosage: Subjects will be treated with 3mg/kg up to a maximum dose of 240mg of nivolumab as an approximate 60 minute IV infusion every 2 weeks.

Immuno-oncology (I-O) agents are associated with adverse events that can differ in severity and duration than adverse events caused by other therapeutic classes. Nivolumab is considered an immuno-oncology agent in this protocol. Early recognition and management of adverse events associated with immuno-oncology agents may mitigate severe toxicity. Immune Toxicities may include:

- Pulmonary (pneumonitis)
- Gastrointestinal (colitis with diarrhea)
- Endocrinopathies (including inflammation of the thyroid, adrenal and pituitary)
- Hepatic (hepatitis)
- Renal (nephritis)
- Skin (rash)
- Neurological (neuritis)

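### Section 5.3(5) orders a nivolumab hold and high-dose steroids for residual immune-mediated toxicities with no entry grade and no thyroid exception, while 5.6 recommends no dosage change for thyroid disorders

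*Protocol*

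**What the plan says.** The heading of Protocol section 5.3 sets the action for every item beneath it: "Hold treatment until recovery to grade 1 or resolution for". Item 5 is the catch-all: "Other immune-mediated toxicities; also administer high-dose systemic corticosteroids followed by a corticosteroid taper (over 1 month". Its neighbours are more specific. The pneumonitis item, for example, reads "Pneumonitis (grade 2); also administer high-dose systemic corticosteroids (prednisone 1 to 2 mg/kg daily or equivalent) followed by a corticosteroid taper".

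Section 5.6 deals with the thyroid in a single line: "Thyroid disorder (hyperthyroidism or hypothyroidism): There are no recommended dosage modifications". It gives no grade limit, does not mention steroids and does not refer to 5.3.

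Section 9.0 (Dosage Forms and Strengths) lists possible immune toxicities of nivolumab, among them "Endocrinopathies (including inflammation of the thyroid, adrenal and pituitary".

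Two other rules bear on dosing. Section 5.1 excludes dose reductions and refers to events "which in the judgment of the investigator, can warrant delaying the dose of study medication". Section 5.2 says that patients with drug-related grade 4 or clinically significant grade 3 toxicity "must have toxicity resolved to grade 2 or less prior to resuming nivolumab".

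**The concern.** Two rules in the same section appear to give different instructions for one event. Take a grade 2 hypothyroidism that the investigator attributes to nivolumab. A site following 5.3(5) would stop the drug and start high-dose steroids. A site following 5.6 would carry on dosing. Each could cite the protocol.

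What is at stake is patient safety and consistency between sites. Section 4.2 bars systemic corticosteroids during the study except for short-term treatment of allergic reactions or immune-related events, so an unneeded course is not trivial here. A patient started on steroids also comes within the scope of 5.4(4), which lists "Inability to reduce corticosteroid dose to prednisone" at or below 10 mg/day within 12 weeks as a reason to discontinue.

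Separately, with no entry grade in item 5, a reader cannot be sure whether low-grade events such as rash are covered.

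**Working it through.** No arithmetic applies; the check is a side-by-side reading.

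| Question | 5.3 heading with item 5 | 5.6 |
|---|---|---|
| Events covered | Residual immune-mediated toxicities; thyroid not named | Hyper- or hypothyroidism |
| Entry grade | None stated | None stated |
| Nivolumab | Hold until grade 1 or resolution | No modification recommended |
| Steroids | High-dose systemic, then one-month taper | Silent |
| Cross-reference to the other rule | None | None |

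1. **Does item 5 reach the thyroid?** Items 1 to 4 and 6 of 5.3 cover liver tests, hepatitis, colitis, pneumonitis and creatinine. The thyroid is named neither there nor in 5.4. Section 9.0 counts thyroid inflammation as an immune toxicity. A thyroid disorder judged immune-mediated is therefore, literally, one of the others.

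2. **Is a hold a dosage modification?** In this protocol, yes. Section 5.1 carries dose modifications in its title, rules out reductions and provides for delay.

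3. **At what grade do the rules differ?** At grade 1 the exit condition in the 5.3 heading is already met, so the hold has no effect. At grade 2 the heading orders a hold and 5.6 recommends no change. Neither 5.2 (grade 4 and clinically significant grade 3) nor 5.4(5) (life-threatening, severe, recurrent or persistent grade 3) applies at grade 2, so that is where the conflict is cleanest.

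4. **What about steroids?** Section 5.6 speaks only of dosage. It neither repeats nor revokes the steroid order, which is left uncancelled.

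5. **Does another rule settle it?** Section 5.1 permits a delay without requiring or forbidding one. Section 5.2 does not reach grade 2, and its resume level is looser than the grade 1 in the 5.3 heading. No order of precedence is written.

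6. **Is an entry grade implied?** Five of the six items in 5.3 state a grade or laboratory trigger; item 5 is the exception. Holding until grade 1 suggests entry at grade 2. But 5.3(6), under the same heading, acts on a grade 1 creatinine rise (above 1.5 times baseline), so the heading does not reliably supply a floor.

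The missing steroid dose is not part of the point. Section 5 mentions high-dose systemic corticosteroids ten times; eight of those give 1 to 2 mg/kg, and the two without a dose are 5.3(5) and 5.4(6).

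**The case against.** The strongest reply is that ordinary reading resolves the matter. Item 5 is a residual category and 5.6 is a rule written for the thyroid; the specific displaces the general. On this view the steroids fall away too, because item 5 adds them to a hold, and with no hold there is nothing to add them to. The list in 9.0 is an awareness list, not a dosing trigger, and it names inflammation where 5.6 names functional disorders. Section 5.6 also only declines to recommend a modification; it does not forbid one.

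Much of this stands. Section 5.6 is the natural governing rule, which makes harm less likely. Nor can the literal reading lean on parallels elsewhere. Hepatotoxicity has its own subsection (5.5) and also appears in 5.3, but it is named there and so never reaches the catch-all. The alopecia exception in 5.4(5) belongs to a discontinuation rule and says nothing about the reach of 5.3(5).

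What does not stand is the claim that nothing needs correcting. The precedence has to be inferred, the fate of the steroid order has to be inferred from one connecting word, and the grade floor from a heading that 5.3(6) does not respect.

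A reader might infer that the protocol requires high-dose steroids for every low-grade immune event, or that 5.6 contradicts the steroid order. The documents support neither: coverage of low-grade events is unclear rather than ordered, and 5.6 does not address steroids.

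**Conclusion.** The inconsistency is real, narrow and minor. It concerns thyroid events above grade 1 that the investigator judges immune-mediated. For these, 5.3(5) with its heading orders a hold, and 5.6 recommends no dosage modification. The steroid order is left standing by silence. The missing entry grade is a second, smaller drafting gap.

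The conclusion rests on a literal reading of 5.3(5), on treating a delay as a dosage modification as 5.1 does, and on 9.0 as the indication that thyroid disorders can be immune-mediated.

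One might be tempted to put a number on patients affected or doses missed. The documents give no thyroid-event rate and no expected hold length, and the section 6.0 calendar schedules TSH only before the study. Any such figure would be assumption, and would not in any case measure how often a site would choose 5.3(5) over 5.6. Nor should one infer frequent discontinuation under 5.4(4): that needs a failure to taper within 12 weeks, against an ordered taper of one month. Nothing here touches the response endpoint or the 18- and 33-patient stages in Protocol section 17.1 and the SAP.

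**What to change.** Amend 5.3(5) by inserting, after its opening words, *of grade 2 or higher not meeting 5.4(5), except hyper- or hypothyroidism (see 5.6)*. Leave its steroid and taper wording unchanged.

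Add to 5.6: *Section 5.3(5), including its corticosteroid order, does not apply; delay remains at investigator discretion under 5.1.*

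Leave 5.4(5) alone, so severe, recurrent or persistent events are still handled there. Do not write 1 to 2 mg/kg into 5.3(5): that would turn unclear wording into a firm dose for every grade 2 non-thyroid event, rash included, which is a separate and debatable clinical choice.

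The cost is a short protocol amendment: one qualified item and one added sentence, with no new assessments and no change to the SAP.
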